Clinical study protocol

Effect of the Teleconsultation of Renal Nutrition on Renal Function and Glycemic Control in Patients With DKD

Protocol number: NCT03344549

Date: 30 october 2022

INTRODUCTION

Diabetic kidney disease (DKD) is the leading cause of end-stage renal disease(1). The progression of diabetic nephropathy can be delayed by optimal glycemic control. Nutritional therapy with sugar control and low protein diets (0.8 g/kg/day) are the most recommended (2) however, it is difficult to achieve compliance (3). The dimensions of chronic kidney disease show it as a public health problem that requires the creation of new interventional and educational programs (4). Telehealth may improve clinical outcomes, care coordination, engagement, and satisfaction.

METHODS

Primary objective

The main goal of the study, a randomized and controlled study, is to determine a difference between the nutritional intervention through teleconsultation and the face-to-face consultation in patients with diabetic kidney disease in stage G3a, G3b and G4.

Study design

The trial will be a prospective, randomized, open, controlled design that will last 4 months. The trial was registered in the clinicaltrials.gov registry (ClinicalTrials.gov identifier: NCT03344549).

Study population

A total of 53 adult volunteers with a diagnosis of DKD will be recruited for this study. To be eligible in the trial, subjects must fulfil all of the inclusion criteria and none of the exclusion criteria, as stated below.

The following inclusion criterio will be adopted:

- (1) Outpatients aged 18–80 years.
- (2) With DKD with eGFR <60 ml / min / 1.73m² and ≥ 15 ml / min / 1.73m², (stage G3a, G3b and G4 respectively).
- (3) Written informed consent to participate in this study before any study-mandated procedure.
- (4) Who have access to the internet and have a computer, tablet or smartphone.
- (5) A willingness and motivation to follow the study protocol.

The exclusion criteria will be as follows:

[figure not shown]
- (1) Outpatients who have received prior nutritional treatment for the control of diabetic kidney disease.
- (2) The use of food supplements and / or keto analogues.
- (3) Diagnosis of anemia or recent transfusions (in the last 3 months).
- (4) With serious complications (chronic infection, septicemia, cancer, HIV, Alzheimer's, uncontrolled heart failure, liver failure, refractory arterial hypertension, etc.).

[figure not shown]
(5) Patients with serious difficulties in communication or intellectual deficit that impedes the ability to understand the intervention.

Reasons for the participant to be discontinued from the study:

- (1) Withdrawal of informed consent.
- (2) Non-attendance at the study visits (≥ 2 nutritional interventions),
- (3) Exclusion criteria found after enrollment, and
- (4) Any serious adverse event during the intervention period (based on data safety monitoring).
- (5) Admission to dialysis

Figure 1. CONSORT Flow Diagram

Sample size calculation

For the calculation of sample size, the formula was used to compare means of independent samples. A size of 27 patients per group was estimated, considering an expected difference in the Glycated Hemoglobin percentage of 0.7 reported in a previous study (6).

Randomization

Randomization was performed using the simple method without replacement with sealed envelopes. Recruited individuals will be allocated into one of two groups:

- (1) Teleconsultation ($n = 26$)
- (2) Face to face consultation ($n = 27$)

DIETARY INTERVENTIONS

The teleconsultation group received nutritional therapy by video call in real time, with a monthly frequency for 4 months. The consultation includes the evaluation or reevaluation, diagnostic treatment and educational approach. Failure to attend more than two consultations is considered an exclusion criterion.

The Face to face consultation group, received nutritional therapy through face-to-face consultations in the hospital with a monthly frequency for 4 months. The consultation includes the evaluation or re-evaluation, diagnosis, treatment and educational approach. Failure to attend more than two consultations is considered an exclusion criterion.

DATA ANALYSIS PRINCIPLES

To determine the difference between the nutritional interventions, the following changes from the baseline (I1) to the end of the study (I6) will be determined as primary outcomes:

- (1) Renal function with de the determination of the changes in the estimated glomerular filtration rate (eGFR)
- (2) Glycemic control with the determination of the changes in the Hemoglobin A1c (HbA1c)

To evaluate the adherence to nutritional interventions were determined as secondary outcome:

- (1) Level of compliance, was assessed using a self-reported Likert scale. Being the score 10 = good adherence and the score 1 = poor adherence to treatment.

STUDY PROCEDURES

The detection of patients is carried out in the nephrology department of the Juan I. Menchaca hospital, both in the morning and afternoon sessions. The identification of patients is carried out during the consultation with the nephrologist, where the selection criteria are evaluated and the patient is invited to participate in the study and to sign the agree consent.

After the patient's acceptance to participate in the study, the initial evaluation is carried out, which includes contact, demographic, anthropometric and dietary data; and the patient is trained to fill the dietary record at home. Anthropometric data are evaluated by standardized nutritionist trained with the correct technique. Venous blood was collected by qualified nurses. The biochemical indicators are requested by the nephrologist at the time of the consultation and the results of these are obtained from the institution's own data system.

After the initial evaluation, the probabilistic group assignment is carried out with the simple method without replacement, which is carried out using a sealed envelope. After the appointment of the group, the patient is scheduled for his first nutrition consultation (both arms).

In the teleconsultation group, two days before the first nutrition consultation, the patient is advised by telephone - or the family member in charge - about the use of the free technological tool to be used during the video conference.

In the patients of the intervention group, the nutritional intervention is carried out through teleconsultation with the free technological tool chosen (the patients from home and the

nutritionist from the remote clinic); and the patients of the control group are offered the nutritional intervention through face-to-face consultations carried out by the nutritionist of the nutrition service of the institution. All patients will be confirmed by phone the date and time of their next nutrition consultation, both the control group and the intervention group (Table.1)

Table 1. Timeline of the study

Time (weeks) from start of dietary intervention	Pre- baseline	Study period						Close- out
		Baseline	(I1)	(I2)	(I3)	(I4)	(I5)	
		(I0)	Week -1	Week 0	Week 4	Week 8	Week 12	Week 16
Screening and sign the agree consent.	x							
Randomization	x							
Socio- demographic data	x							
Blood serum measurements	x							x

Dietary habits	x						x
Anthropometric measures	x						x
Nutritional intervention		x	x	x	x	x	
Level of compliance			x	x	x	x	

Data collection

The following clinical/dietary information was obtained:

- Socio-demographic data (a questionnaire).
- Dietary habits: a 3-day food record.
- Vital signs: blood pressure.
- Anthropometric measures: weight, height, body mass index (BMI).
- Gastrointestinal symptoms: frequency and duration.

In the blood serum, we evaluated markers of glucose, and hemoglobin A1c; serum creatinine, urea, albúmin and blood biometry.

STATISTICAL ANALYSIS PLAN

Categorical variables are presented as numbers and percentages, and comparisons between groups were performed with the chi-square or Fisher exact test as appropriate. According to

the Shapiro–Wilk test for data distribution, continuous variables are summarized as the means \pm standard deviations (SD) if normally distributed or medians and interquartile ranges (25–75th) if non-normally distributed and were compared using Student’s t-test or the Mann–Whitney U test, respectively. For variables measured at multiple time points, repeated measures analysis of variance tests were used for the comparisons between groups. For the analysis of the interaction or intervening variables, a stratified statistical analysis will be carried out, using contingency tables and the Mantel-Haenszel method. All tests were two-tailed, and a p value less than 0.05 were considered significant. Statistical analysis and graphics were performed with IBM® SPSS® Statistics Ver. 22).

ETHICS APPROVAL AND CONSENT TO PARTICIPATE

The trial was conducted in accordance with the principles of the Declaration of Helsinki and the International Conference on Harmonization Guidelines for Good Clinical Practice. All patients gave their written informed consent before any study-related procedure. The study was approved by the local ethics committee (14 CEI 14 039 048), was prospectively registered in clinicaltrials.gov (NCT03344549). No funding was received to conduct this study. The clinical trial was carried out under the CONSORT guidelines.

Informed consent was obtained from all subjects. All methods were carried out in accordance with relevant guidelines and regulations. All experimental protocols were approved by the Institutional Review Board “Comité de ética en Investigación del OPD Hospital Civil de Guadalajara [name]”

CONSENT FOR PUBLICATION

REFERENCES

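### Serious adverse events and dialysis remove patients from the study, but no visit is scheduled to record them and no analysis reports them by arm

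*Combined protocol and SAP*

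**What the plan says.** Under "Reasons for the participant to be discontinued from the study" the protocol gives five reasons. Three matter here: reason (2), "Non-attendance at the study visits (≥ 2 nutritional interventions"; reason (4), "Any serious adverse event during the intervention period (based on data safety monitoring"; and reason (5), "Admission to dialysis". The exit is from the study, not only from the dietary intervention.

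The timeline in Study Procedures ("Table 1. Timeline of the study") has eight rows: screening and consent, randomisation, socio-demographic data, blood measurements, dietary habits, anthropometry, nutritional intervention and compliance. The blood row carries two marks, one before the intervention and one at the end.

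The Data collection section comes nearest to harms with "Vital signs: blood pressure" and "Gastrointestinal symptoms: frequency and duration". Neither has a row in the timeline, and neither is called a safety measure.

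The outcomes under Data Analysis Principles are change in eGFR, change in HbA1c and self-reported compliance. The SAP has a general sentence on chi-square or Fisher tests for categorical variables and does not mention adverse events.

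**The concern.** Reason (4) depends on information that the plan gives no route for obtaining. A site following the timeline asks no one, at any visit, whether a serious event has occurred. What it learns then depends on spontaneous mention, on missed appointments, or on what staff happen to see. In an open trial whose arms differ in setting and staff, those channels need not work equally well in both.

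Two things are at stake. First, a difference between arms in recorded serious events, and in removals under reason (4), could reflect detection rather than risk. Second, the trial enrols patients with eGFR from 15 to below 60, for whom starting dialysis is a direct renal outcome. Yet dialysis and serious events feature only as reasons to leave, so the trial could report on eGFR and HbA1c without stating how many such events each arm had.

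This is separate from the question of which patients enter the eGFR and HbA1c analyses.

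**Working it through.** The only computed figure in the plan is the 27 per group for HbA1c. It has no bearing on this point, and there is no safety figure to reproduce. The check is therefore mainly a reading of the text, followed by an illustration.

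**1. Following a serious event through the plan**

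- Discontinuation list: named, as a reason to leave.
- Definition, responsible body, reporting route: none given.
- Timeline: no row.
- Data collection list: no serious events, admissions or dialysis starts.
- Primary and secondary outcomes: none.
- SAP: no named tabulation or comparison.

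Dialysis follows the same path.

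**2. How contact differs by arm**

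- Same in both: monthly consultations for 4 months, and a call before each ("All patients will be confirmed by phone the date and time of their next nutrition consultation").
- Different: face-to-face patients attend the hospital and see its own nutrition service; teleconsultation patients are at home, with a nutritionist at a remote clinic.

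Unequal detection is possible on these facts. Neither its existence nor its direction follows from them.

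**3. Overlapping reasons**

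A patient in hospital through two consultations meets both reason (2) and reason (4), and no precedence is stated. The non-attendance threshold also varies. The discontinuation list sets it at two or more missed interventions; Dietary Interventions sets it above two. A patient who misses exactly two meets the first and not the second.

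**4. Illustration (risk and detection rates are assumptions; only 26 and 27 come from the plan)**

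Expected recorded events = patients × true risk × fraction detected. The true risk is the same in both arms.

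| True risk | Detection, tele v face-to-face | Tele (26) | Face-to-face (27) |
|---|---|---|---|
| 15% | 90% v 90% | 26 × 0.15 × 0.9 = 3.51 | 27 × 0.15 × 0.9 = 3.65 |
| 15% | 70% v 90% | 26 × 0.15 × 0.7 = 2.73 | 3.65 |
| 15% | 50% v 90% | 26 × 0.15 × 0.5 = 1.95 | 3.65 |
| 15% | 90% v 50% | 3.51 | 27 × 0.15 × 0.5 = 2.03 |
| 10% | 50% v 100% | 26 × 0.10 × 0.5 = 1.30 | 27 × 0.10 = 2.70 |

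With equal detection the arms look alike. In the third row the recorded risks are 1.95/26 = 7.5% and 3.65/27 = 13.5%, a gap of 3.65 − 1.95 = 1.7 patients produced by detection alone. The fourth row reverses the direction.

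**5. What 53 patients can show, even with complete detection**

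- No events at all leaves a one-sided 95% upper bound of 1 − 0.05^(1/26) = 10.9% for teleconsultation and 1 − 0.05^(1/27) = 10.5% for face-to-face.
- Exact power of a two-sided Fisher test at 0.05 (teleconsultation risk first): 3% for 10% v 5%; 28% for 20% v 5%; 64% for 30% v 5%; 17% for 15% v 30%.
- Observed counts of 2/26 v 4/27, close to the third row above, give Fisher p = 0.67.

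A test will seldom settle anything here. Complete counts with exact intervals are what the trial can offer.

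**The case against.** The strongest reply is that this is a gap in description and reporting, not a demonstrated bias. Contact is monthly in both arms, each consultation includes an evaluation or re-evaluation, and both arms get the confirmation calls. The control contact is with a nutritionist and is not a safety visit. A reader might infer that harms are in fact detected less often in the teleconsultation arm. The documents do not support that: no passage says so, and the detection fractions above are assumed.

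A reader might also infer that no monitoring exists, or that events will vanish as unexplained attrition and never be reported. That too goes beyond the text. The protocol refers to monitoring and to Good Clinical Practice, so the monitoring is undescribed rather than shown to be absent. Serious events and dialysis are separately named reasons. The protocol includes a CONSORT flow diagram, whose content is not visible here, and says the trial follows CONSORT guidelines, so discontinuations by reason may appear by arm. The general chi-square or Fisher sentence could also be applied to them.

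Misfiling under non-attendance is likewise a possibility rather than a finding, since nothing ranks reason (2) above reason (4). Finally, both arms receive nutritional therapy and differ mainly in how it is delivered, so the absence of a safety outcome does not invalidate the planned comparison.

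All of that stands. It leaves the core untouched: nothing commits the trial to looking for these events in the same way in both arms, or to reporting them by arm.

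**Conclusion.** The point holds in a limited form. The plan removes patients for serious adverse events and for dialysis without scheduling any collection of either, and without an outcome or analysis that reports them by arm. Detection, and hence removal under reason (4), may differ between arms, and nothing ensures that the events enter the conclusion.

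The documents do not allow the size to be estimated. Under the assumed risks of 10% to 15%, detection differing by 20 to 50 percentage points shifts the recorded counts by about one to two patients in either direction; equal detection shifts them hardly at all. With 26 and 27 patients, that is enough to alter how a safety table reads, though not to produce a significant test.

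This is a worthwhile and inexpensive improvement, not a defect that undermines the eGFR or HbA1c comparison. The reading rests on the timeline rows, the data collection list, the outcomes and the SAP, all of which are legible; the flow diagram is not shown.

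**What to change.** - **Collection.** Add an adverse-event row to the timeline. Ask the same scripted questions in both arms (hospital admission, dialysis start, other serious event, gastrointestinal symptoms) on the confirmation calls already made. Ask them again at the close-out assessment, because those calls precede consultations and none is documented for the period after the last one.
- **Record search.** At close-out, search the institution's data system, already used for laboratory results, for admissions, dialysis and death. Cover all randomised patients, including those discontinued, except any whose withdrawal of consent extends to record access. Where an event caused the non-attendance, record both reasons.
- **Reporting.** Tabulate serious events, dialysis starts and discontinuations by reason and randomised arm, as counts with exact confidence intervals. Treat this as descriptive, with any Fisher test secondary.
- **Consistency.** Describe the monitoring that reason (4) cites and reconcile that reason with the timeline. Reconcile the two non-attendance thresholds. Which clinical rule applies is for the sponsor to decide.

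The documents mix past and future tense, so follow-up may be over. In that case the scripted questions can no longer be asked, but the record search and the table can still be done.

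The cost is a few minutes on calls already planned, one record search per patient, one table and a short amendment. The drawbacks are slightly more data entry and that the search will miss care given at other hospitals.

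### Non-attendance removes patients but is never counted, so the only adherence outcome can favour whichever arm loses more non-attenders

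*Combined protocol and SAP*

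**What the plan says.** DATA ANALYSIS PRINCIPLES introduces the secondary outcome with "To evaluate the adherence to nutritional interventions were determined as secondary outcome" and lists a single item: "Level of compliance, was assessed using a self-reported Likert scale. Being the score 10 = good adherence", with 1 at the poor end.

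Attendance appears only as a ground for removing patients, in two places:

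- Under the heading "Reasons for the participant to be discontinued from the study", one ground is "Non-attendance at the study visits (≥ 2 nutritional interventions".
- DIETARY INTERVENTIONS says of each arm: "Failure to attend more than two consultations is considered an exclusion criterion".

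Table 1 marks the nutritional intervention five times and "Level of compliance" four times. The columns are disturbed by text extraction, but in the order of the marks each rating falls on a visit that also carries a consultation.

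The STATISTICAL ANALYSIS PLAN compares repeatedly measured variables between groups by repeated-measures analysis of variance. It defines no analysis set, no handling of missing ratings and no comparison of attendance. A food record is kept, but it is not named as an adherence outcome.

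The INTRODUCTION gives the background rationale: "Telehealth may improve clinical outcomes, care coordination, engagement, and satisfaction".

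**The concern.** The arms differ in how a consultation is attended: from home by video, or at the hospital. Attendance is therefore something the intervention may itself change, yet the plan uses it after randomisation to decide who stays. A patient who misses a consultation gives no rating at that visit, and one who is discontinued gives none afterwards.

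If those patients adhere less than average, the ratings that remain are too favourable, and more so in the arm that loses more people. At stake is the trial's only conclusion on adherence. An arm that holds on to its less adherent patients would have them rated and could look worse for it, while the better attendance that kept them would appear in no outcome.

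**Working it through.** **Figures in the documents.** There are none on attendance, dropout or the distribution of the compliance score, so there is no planned figure to reproduce. The sample size of 27 per group concerns HbA1c and has no bearing here. Everything below illustrates the mechanism.

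**From the documents.** Five consultations and four ratings (Table 1); removal at 2 or more missed, or at more than two missed (both are stated); 26 + 27 = 53 randomised.

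**Assumed.** True adherence is the same in both arms, normal with mean 6.5 and SD 2. Each of the five consultations is missed independently with probability p, where logit(p) = logit(p0) + b × (adherence − 6.5). The base case has p0 = 0.20 face to face, p0 = 0.10 by video and b = −0.4. Ratings equal true adherence and are given at attended visits among the last four. Which arm has the higher miss rate is arbitrary; swapping the arms reverses the sign.

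**Step 1: who remains.** With removal at 2 or more missed, 68% remain face to face and 86% by video. Their mean scores are 7.17 and 6.81, a spurious gap of 7.17 − 6.81 = 0.36.

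**Step 2: threshold and ratings used.** Spurious gap in favour of the arm that loses more:

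| Ratings analysed | Removal at 2 or more missed | Removal at more than two missed |
|---|---|---|
| Patients with all four ratings | 0.42 | 0.42 |
| Patients not removed | 0.36 | 0.21 |
| All available ratings, pooled | 0.24 | 0.18 |
| One mean per patient with any rating | 0.14 | 0.08 |

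The first row is what classical repeated-measures analysis of variance uses. It is the same under both thresholds because a patient with all four ratings has missed at most one consultation. The lower rows are smaller because about 65% (face to face) and 71% (video) of removed patients have at least one rating under the first threshold.

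**Step 3: other inputs, patients not removed.**

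- Weaker link (b = −0.2): 0.23 at 2 or more missed, 0.10 at more than two.
- Smaller difference between arms (20% versus 15%): 0.18 and 0.11.
- Larger difference (20% versus 5%, first threshold): 0.54.
- Equal miss rates, or no link (b = 0): zero.

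Combining the weaker link, the second threshold and per-patient means gives less than any figure in the table.

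**Step 4: check by another route.** If the lowest fraction q of an attendance variable is removed, and that variable has correlation ρ with the score, the mean of those kept rises by ρ × SD × φ(z_q) / (1 − q). Take SD 2, ρ = 0.5 and losses of 25% and 5%:

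- 25%: 0.5 × 2 × 0.3178 / 0.75 = 0.424
- 5%: 0.5 × 2 × 0.1031 / 0.95 = 0.109
- Difference: 0.424 − 0.109 = 0.32 (rounded from 0.315)

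The same sum gives 0.19 at ρ = 0.3, 0.44 at ρ = 0.7 and 0 at ρ = 0. With 26 and 27 patients, a score with mean 7 rounded and limited to 1–10, and a two-sided test at 0.05, the simulated false-positive rate at these losses was 4.9% (ρ = 0), 8.3% (ρ = 0.5) and 24.0% (ρ = 1). The sign can change: with ρ = 0.7, an arm that is truly 0.3 points worse and loses the 25% appears better by 0.44 − 0.30 = 0.14. If it is truly 0.5 worse, it still appears worse, by 0.06.

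**The case against.** The strongest reply is that both size and direction rest on assumed inputs. That stands. Video consultation needs a device and a software tool, so it could be missed more often, not less. The plan also limits unequal attendance: appointments in both arms are confirmed by phone, video patients are instructed beforehand, and entry requires internet access and motivation. A reader might infer that teleconsultation will wrongly appear to have poorer compliance. The documents do not support that; they support only a bias towards whichever arm loses more, if the two conditions hold.

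A reader might also infer that removed patients contribute no ratings, so that no analysis could help. That is wrong. Removal follows at least two missed consultations, and ratings given earlier exist. Much of the gap therefore comes from complete-case analysis. It does not all come from there, as the pooled row of the table shows.

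Dietary adherence and attendance are different constructs, and the rationale mentions engagement only as background. This stands as a reason to report attendance beside the self-rating rather than in its place.

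Finally, the protocol includes a CONSORT flow diagram (not visible here) and commits to the CONSORT guidelines, so losses by arm cannot be assumed to go unreported. A count of losses is still not an attendance outcome.

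**Conclusion.** The concern holds in conditional form. The only adherence outcome is observed at attended consultations, and the plan's own rule removes those who do not attend. Bias between arms needs non-attenders to adhere less and non-attendance to differ by arm. Given both, with a 20% versus 10% miss probability and equal true adherence, it is about 0.1 to 0.4 points; without either, it is zero. The real size and direction cannot be known from the documents. Using all available ratings lessens the bias but does not cure it.

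The two attendance thresholds contradict each other, so who is removed is not fixed. The matter concerns a secondary outcome and does not touch the definitions of the primary outcomes, eGFR and HbA1c. The change is worth making because it is cheap and protects the trial's only adherence conclusion.

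**What to change.** In DATA ANALYSIS PRINCIPLES:

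- Add consultations attended, out of those scheduled, as a secondary engagement and adherence outcome, compared by arm in all 53 randomised patients.
- State the counting rule. For patients discontinued for dialysis, a serious adverse event or withdrawn consent, count only consultations scheduled up to that date. Count consultations lost through the non-attendance rule as not attended. The rule matters: under the base case with removal at 2 or more missed, mean attendance out of five is 3.56 versus 4.26 when counted this way, but 3.87 versus 4.39 if patients are imagined to continue after removal.
- Report the number discontinued for non-attendance in each arm.
- Analyse all available Likert ratings, including those given before removal, describe them as compliance at attended visits, and draw no adherence conclusion from them alone.

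The discontinuation list and DIETARY INTERVENTIONS must be reconciled on the attendance threshold. The attendance count is needed whichever wording stands.

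The cost is a change of wording and one comparison on data already needed to operate the attendance rule. The downside is one more secondary comparison and a narrower compliance claim.

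### Practical ability to use the video tool is not checked before randomisation, which creates a risk of differential loss between the arms after allocation

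*Combined protocol and SAP*

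**What the plan says.** Two eligibility criteria under Study population bear on technology and communication, and both apply to every candidate. Inclusion criterion (4) reads "Who have access to the internet and have a computer, tablet or smartphone". Exclusion criterion (5) reads "Patients with serious difficulties in communication or intellectual deficit that impedes the ability to understand the intervention". Study Procedures places this check at the nephrology consultation, "where the selection criteria are evaluated and the patient is invited to participate in the study".

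The initial evaluation that follows covers contact, demographic, anthropometric and dietary data and training in the food record. No trial of the video tool is listed. The envelope comes next: "After the initial evaluation, the probabilistic group assignment is carried out with the simple method without replacement". Then "After the appointment of the group, the patient is scheduled for his first nutrition consultation (both arms". Only after that, and only for one arm, does the text turn to using the tool: "In the teleconsultation group, two days before the first nutrition consultation, the patient is advised by telephone". The advice may go instead to a relative ("or the family member in charge").

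The listed reasons for discontinuation include "Non-attendance at the study visits (≥ 2 nutritional interventions". Dietary Interventions says of each arm, in the same words, that missing more than two consultations is an exclusion criterion. These two thresholds conflict and must be reconciled.

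The Statistical Analysis Plan names no as-randomised analysis set and no rule for missing outcomes. Table 1 schedules blood measurements once before the intervention and once at the end.

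**The concern.** Having a smartphone and a connection is not the same as being able to complete a video consultation from home, and the age limit runs to 80. The protocol plans advice on the tool, so it does not itself assume that patients can use it. That ability exists before randomisation, but under this sequence it can show itself only in the teleconsultation arm. There it would appear as missed consultations, which the plan answers by removal under either threshold once enough are missed. In the face-to-face arm the same trait has no occasion to appear.

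If patients who struggle with the tool also tend to have different HbA1c or eGFR changes, removing them from one arm breaks the balance that randomisation created. With about 26 patients in that arm, a handful of such losses matters. With no as-allocated analysis stated, and no stated plan to obtain final bloods from discontinued patients, nothing in the plan limits the effect.

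**Working it through.** **Order of events.** (1) Eligibility check, both arms. (2) Consent and initial evaluation, both arms, with no test of the tool. (3) Sealed envelope. (4) First consultation scheduled, both arms. (5) Tool advice, teleconsultation arm only. (6) Monthly consultations, with removal for repeated absence in both arms. Practical ability is therefore not checked at any step before (3).

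**Inputs from the documents.** 26 teleconsultation and 27 face-to-face patients (Randomization); HbA1c difference of 0.7 and 27 per group (Sample size calculation); two-sided 0.05 (Statistical Analysis Plan).

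**Assumed, because the documents do not give them.** Share f of patients who cannot connect and are lost: 5% to 20%. Amount g by which their mean HbA1c change is worse: 0.5 to 1.0 points. No comparable loss in the face-to-face arm. SD of 0.90.

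**The plan's own figure.** The 27 per group cannot be reproduced, since SD and power are not stated. Assuming 80% power, the normal formula gives SD = 0.7 / (1.960 + 0.842) × √(27/2) = 0.918. The noncentral t gives 0.901, which is the source of the 0.90 used here.

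**Bias with no true effect.** Let m be the mean change among patients who can connect. After the loss, the teleconsultation mean is m. The face-to-face arm keeps its share f, so its mean is m + f·g. The spurious difference is f × g.

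**Type I error.** Standard error = 0.90 × √(1/27 + 1/n), where n is the number left in the teleconsultation arm. The rejection probability is from the noncentral t with non-centrality f·g / standard error and 27 + n − 2 degrees of freedom.

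| f | 26 × f | n left | bias, g = 0.5 | bias, g = 1.0 | type I error, g = 0.5 | type I error, g = 1.0 |
|---|---|---|---|---|---|---|
| 5% | 1.3 | 25 | 0.025 | 0.05 | 5.1% | 5.4% |
| 10% | 2.6 | 23 | 0.05 | 0.10 | 5.4% | 6.7% |
| 15% | 3.9 | 22 | 0.075 | 0.15 | 5.9% | 8.8% |
| 20% | 5.2 | 21 | 0.10 | 0.20 | 6.6% | 11.6% |

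As a share of 0.7, the bias runs from 0.025/0.7 = 4% to 0.20/0.7 = 29%. In the bottom row at g = 1.0, the standard error is 0.90 × √(1/27 + 1/21) = 0.262 and the non-centrality is 0.20/0.262 = 0.76. With f = 0 or g = 0 the bias is zero.

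**The case against.** The sequence looks worse than it is. The telephone call is support, not a test, and should reduce connection failure. A relative can help. Inclusion criterion (5) also asks for willingness to follow the protocol. One failed first call removes nobody under either attendance rule, and monthly spacing leaves about four weeks to solve a problem. All of this stands, and it limits how many patients are likely to be lost.

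A reader might infer that patients who cannot connect are screened out at the advice call. No text says so, and no rule is given for such a patient. The route to loss is through later non-attendance.

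A reader might also infer that loss falls on one arm only and tilts the result toward teleconsultation. The attendance rule is worded identically for both arms, and face-to-face patients must reach the hospital every month. Poorly supported patients may fail to do so. What remains is that the reasons differ by arm and need not cancel.

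A third tempting step is to shrink the 0.7 by the share not connecting and quote a loss of power. That does not follow. The comparison arm receives active nutritional therapy, so a teleconsultation patient who gets no consultations cannot be assumed to do as well as a face-to-face patient. The size of the face-to-face benefit is not given.

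The strongest counter-argument is that analysing everyone as allocated, with outcomes obtained, keeps the arms comparable, and that failure to connect is then part of what offering teleconsultation achieves. That is right, but the plan neither states such an analysis nor provides for those outcomes. Finally, even the largest bias above, 0.20, is smaller than one standard error with all patients present: 0.90 × √(1/26 + 1/27) = 0.25.

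**Conclusion.** The point holds as a risk of differential post-randomisation loss. The documents establish three things: practical use of the tool is not checked before allocation, it is first taken up afterwards in one arm, and repeated absence leads to removal with no as-randomised analysis set stated. They do not establish that the arms cease to be comparable. That depends on a failure rate, an outcome gap and a pattern of face-to-face loss that are all unknown.

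Within the assumed ranges the effect goes from negligible to a type I error more than twice the nominal 5%. The upper end requires one patient in five to be lost with a gap of a full HbA1c point and no offsetting loss, and the direction would reverse if those patients did better rather than worse. This is a moderate point that should be corrected because the remedy is cheap.

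**What to change.** Before the envelope is opened:

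- Give the tool advice and a short test call to every candidate, on the patient's own device and with the helping relative where there is one. Make the call from home if feasible, because an on-site test may not reveal a home connection problem.
- Reword inclusion criterion (4) to require, besides internet access and a device, a test video call completed by the patient or the helping relative.
- Log and report the candidates not randomised for this reason.

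In the follow-up and analysis plan:

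- Analyse all randomised patients as allocated.
- Seek the week 16 bloods regardless of attendance.
- Report reasons for missed consultations by arm, including travel and hospital access for face-to-face patients.
- Reconcile the two non-attendance thresholds.

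The cost is about 27 extra short calls, since the advice call is already planned for the 26 teleconsultation patients, plus the effort of obtaining final bloods from non-attenders. The result would apply to people able to use video calls, which narrows somewhat the population that criterion (4) already aims at. The advice call two days before the first consultation can stay as a reminder.
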